8.7 Disease Free Survival

Disease-Free Survival (DFS) is defined as the interval from complete tumour surgical excision date (with pathology results negative for malignant disease within 1 mm of surgical margins) to date of first occurrence of the events in the table below.

Patients not meeting the criteria for failure by the analysis data cutoff date will be censored at their last disease assessment date.

First Event	Disease Free Survival
None	Censored
Locoregional relapse	Failure
Distant disease	Failure
Non-protocol radiotherapy, chemotherapy or biologic therapy without documentation of the site of failure	Failure
Death due to any other reason	Failure

8.7.1 Capture of Failures and Work-up at Detection of First Failure:

Only the first event experienced will determine a patient's failure status for DFS analysis. However, in order to fully capture the patterns of failure in this study population, a detailed work-up at the time of the first failure is required, and sites of failures should be documented in the CRF.

For instance, if a patient first develops locoregional relapse, then a work-up for distant metastasis will be performed at the same time. If the distant metastatic work-up reveals the presence of distant metastasis, then all sites of failure will be documented, even though the time of the first detected failure event will be used to determine the disease free survival. Similarly, if a patient is first found to have distant metastasis, then a work-up for locoregional relapse should be performed at the same time. If the locoregional work-up does not reveal relapse at the same time, then this patient is considered to only have distant disease failure.

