APPENDIX III - DOCUMENTATION FOR STUDY

Follow-up is required for patients from the time of enrollment and will apply to all eligible and ineligible patients. This trial will use a web-based Electronic Data Capture (EDC) system for all data collection including SAE reporting (see Section 9.0 for details regarding SAE reporting). For details about accessing the EDC system and completing the on-line Case Report Forms, please refer to the Data Management Guidebook posted on the CO.28 area of the CCTG web-site (www.ctg.queensu.ca).

The ELECTRONIC CRFs to be used in this trial are:

Electronic Case Report Form	To be Completed/Submitted Electronically:	Supporting Documentation to be sent using Supporting Document Upload Tool*
BASELINE REPORT	Due within 2 weeks of patient enrollment.	Copies of signature pages of main and optional consent forms; relevant pathology & radiology reports.
CHEMOTHERAPY REPORT	To be completed after each chemotherapy cycle. Due within 2 weeks of end of cycle. This report documents treatment, adverse events and investigations for each chemotherapy cycle.	Relevant radiology reports.
PRE-EXCISION VISIT REPORT	To be complete within 2 weeks after pre-excision visit.	Relevant radiology reports.
END OF TREATMENT REPORT	To be complete within 4 weeks after final tumour excision	
SURGERY REPORT	To be complete within 4 weeks after surgery (either TME or TEMS/TAMIS)	Relevant pathology and surgery reports.
CORRELATIVE STUDIES	See Section 12 in this protocol.	Relevant pathology reports.
FOLLOW-UP REPORT	Continued follow-up after chemotherapy, radiotherapy and/or protocol tumour excision(s) completed. Due within 2 weeks after contact with patient.	Relevant pathology, radiology and surgery reports.
RELAPSE REPORT	To be completed at the time of disease relapse or failure. Due within 2 weeks after contact with patient.	Relevant pathology, radiology and surgery reports.
SHORT FOLLOW REPORT	To be completed after disease relapse or failure and for patients that have no protocol tumour excision.	
DEATH REPORT**	Required for all patients while study is open. Due within 2 weeks of knowledge of death.	Autopsy report, if done.

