Kaplan-Meier method (**Figure 2**) will be used to estimate the 3 year loco-regional relapse rate and associated 95% confidence interval first among all patients treated with FOLFOX or CAPOX and TEMS or TAMIS (**Table 31**) and additionally among all patients that have received neoadjuvant chemotherapy.

7.7.3 3 Year Distant Relapse Rate

Distant relapse is defined as appearance of rectal cancer disease at sites remote from the rectum. The number of patients with each site of distant relapse (Lung, Liver, Brain, Distant lymph nodes, Bone, Skin, Ascites, Pleural effusion, Adrenal glands, Other) will be summarized (**Table 31**).

Distant relapse free survival is calculated as time from complete tumour surgical excision date (with pathology results negative for malignant disease within 1 mm of surgical margins) to the first date of definitive evidence (clinical, radiological or pathological) of distant relapses. Patients died, loss to follow up, or alive at clinical cut-off will be censored at respectively date of death, date of lost to follow-up, and last disease assessment date calculated as the last of dates of attendance/last contact on CRD Follow-up Report.

Kaplan-Meier method (**Figure 3**) will be used to estimate the 3 year distant relapse rate and associated 95% confidence interval first among all patients treated with FOLFOX

or CAPOX and TEMS or TAMIS (**Table 31**) and additionally among all patients that have received neoadjuvant chemotherapy.

7.7.4 3 year Disease Free Survival

Disease-Free Survival (DFS) is defined as the interval from complete tumour surgical excision date (with pathology results negative for malignant disease within 1 mm of surgical margins) to date of first occurrence of the events in the below.

- Locoregional relapse reported in CRF Relapse Report
- Distant disease reported in CRF Relapse Report
- Non-protocol radiotherapy, chemotherapy, or biologic therapy without documentation of the site of failure and reported in CRF Chemotherapy Report, Pre-Excision Report, and Surgery Report
- Death due to any other reason reported in CRF Death Report

Patients who are alive without locoregional or distant relapse or receiving non-protocol radiotherapy, chemotherapy, or biologic therapy without documentation of the site of failure at the analysis data cutoff date will be censored at their last disease assessment date calculated as the last of dates of attendance/last contact on Follow-up Report.

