7.8.1 Adverse Events

Adverse events (AEs) are recorded in the Adverse Events (AE) sections of CRF Chemotherapy Report, CRF Pre-Excision Report, CRF Surgery Report, CRF Follow Up Report (only AEs thought to be related to protocol treatment), and CRF Short Follow Up Report (ongoing or new grade 3 or higher AEs which are thought to be related to protocol treatment). Severity grade 5 will be combined with grade 4 for the purpose of this report. Adverse events reported during study treatment (in AE sections of CRF Chemotherapy Report, CRF Pre-Excision Report, and CRF Surgery Report) are defined as acute (on treatment) adverse events. Adverse events reported in AE section of CRF Follow Up Report and CRF Short Follow Up Report will be defined as delayed (long term) AEs.

Treatment (capecitabine, oxaliplatin, leucovorin, surgery, and radiotherapy) related adverse events are those events with a relation to protocol therapy of 3=possible,

4=probable or 5=definite.

Severe adverse events are those events reported with a NCI CTCAE Grade of 3 or higher.

The following variables are summarized:

- Acute adverse events: worst CTCAE grade per patient (**Table 32**)
- Severe acute adverse events: worst CTCAE grade per patient (**Table 33**)
- Treatment related acute adverse events: worst CTCAE grade per patient (**Table 34**)
- Delayed severe adverse events: worst CTCAE grade per patient (**Table 35**)

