7.9 Concomitant Medications and Other Anti-Cancer Treatments

Concomitant medication is defined as medication, other than protocol therapy, which is taken by patients any time on treatment or after end of treatment. Patients may also receive any other anti-cancer treatment during or after being taken off protocol treatment.

- Concomitant medications for patients during protocol treatment (reported on Chemotherapy Report, CRF Pre-Excision Report, and CRF Surgery Report) (**Table 46**)
- Concomitant medications for patients 30 days after excision (reported on CRF Follow-Up Report) (**Table 46**)
- Anti-cancer treatments for patients during protocol treatment (reported on Chemotherapy Report, CRF Pre-Excision Report, and CRF Surgery Report) (**Table 47**)
- Anti-cancer treatments for patients after protocol treatment but before relapse (reported on Follow-Up Report) (**Table 47**)
- Anti-cancer treatments for patients after relapse (reported on Short Follow-Up Report) (**Table 47**)

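### SAP 7.7.4 reads the non-protocol-therapy DFS failure only from treatment-period forms, and SAP 7.7.2 and 7.7.3 date relapse by a different rule from protocol 8.4 and 8.6

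*SAP*

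**What the plan says.** **DFS event.** Protocol 8.7 measures DFS from complete excision and lists as a failure: "Non-protocol radiotherapy, chemotherapy or biologic therapy without documentation of the site of failure". It names no form. SAP 7.7.4 keeps the same time origin and the same event, but requires it to be "without documentation of the site of failure and reported in CRF Chemotherapy Report, Pre-Excision Report, and Surgery Report". It takes locoregional and distant relapse from the Relapse Report and uses the Follow-up Report only for the censoring date.

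**What the forms cover.** SAP 7.9 describes the three listed forms this way: "Anti-cancer treatments for patients during protocol treatment (reported on Chemotherapy Report, CRF Pre-Excision Report, and CRF Surgery Report". SAP 7.8.1 groups the same three for acute toxicity: "Adverse events reported during study treatment (in AE sections of CRF Chemotherapy Report, CRF Pre-Excision Report, and CRF Surgery Report". For later therapy SAP 7.9 names another form: "Anti-cancer treatments for patients after protocol treatment but before relapse (reported on Follow-Up Report". Protocol Appendix III agrees on the scope of the Follow-Up Report: "Continued follow-up after chemotherapy, radiotherapy and/or protocol tumour excision(s) completed".

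**Relapse date.** SAP 7.7.2 and 7.7.3 end the locoregional and distant time-to-event at the first date of definitive evidence. Protocol 8.4 dates locoregional relapse at the first evidence. Protocol 8.6 dates a recurrence found on radiographs or scans from the first suspicious record, even when confirmation comes later.

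**The concern.** A programmer following SAP 7.7.4 literally would look for the therapy event on forms that mostly close before, or soon after, the DFS clock starts. A patient who begins non-protocol therapy during surveillance, with no site documented, would be a failure under the protocol but would not meet the SAP's listed event. That would overstate 3-year DFS.

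The dating difference works in the same favourable direction. A relapse first suspected before 3 years and confirmed after 3 years counts in the 3-year locoregional relapse rate (LRR) or distant relapse rate (DRR) under the protocol's date, but not under the SAP's.

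The three 3-year outcomes are named secondary objectives in both documents. The cohort is small, so a single patient is visible in the estimate.

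**Working it through.** The documents state no expected 3-year DFS, LRR or DRR, so there is no plan figure to reproduce. The check compares the texts and then sizes one affected patient.

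**1. Which form can hold the DFS event?** Time zero is complete excision (protocol 8.7, SAP 7.7.4).

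| Form | Period covered | Source for this event in SAP 7.7.4? |
|---|---|---|
| Chemotherapy Report | each chemotherapy cycle, normally before time zero | yes |
| Pre-Excision Report | pre-excision visit, normally before time zero | yes |
| Surgery Report | due within 4 weeks "after surgery (either TME or TEMS/TAMIS" (a submission deadline; the data window is not stated) | yes |
| Follow-Up Report | after treatment and excision, before relapse | no |
| Relapse Report | "To be completed at the time of disease relapse or failure" | no; used only for locoregional and distant relapse |

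A limited route remains. If TEMS/TAMIS was the complete excision and a TME follows, the second Surgery Report could record therapy given between the two operations. Nothing listed clearly reaches the surveillance period.

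**2. Trace one patient.** The patient has a complete excision, enters surveillance, and starts non-protocol chemotherapy at month 24 with no site documented. The therapy is recorded on the Follow-Up Report.
- Protocol 8.7: failure.
- SAP 7.7.4 event list: not an event, because the source form is not listed.
- SAP 7.7.4 censoring sentence: it covers patients without relapse and without such therapy, and names no form, so it does not clearly cover this patient.
- SAP 7.7.4 reasons for censoring: only alive at cut-off or lost to follow-up.

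The patient is neither a listed event nor clearly censored.

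**3. Size of one missed failure.** Ignoring censoring, the shift is 100/n percentage points. Protocol 13.3 gives 58 in total and 50 evaluable; 40 is an assumed smaller TEMS/TAMIS set.
- n=58: 100/58 = 1.7
- n=50: 100/50 = 2.0
- n=40: 100/40 = 2.5

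With censoring, the Kaplan-Meier step at the event is the current survival estimate divided by the number at risk, so the shift depends on when censoring falls. Illustration, all assumed: n=50, five other events evenly spaced over months 6 to 33, one failure at month 24 that is either counted or missed, and a missed patient followed past month 36.

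| Censoring (evenly spaced) | At risk at month 24 | 3-year DFS, counted | 3-year DFS, missed | Shift (points) |
|---|---|---|---|---|
| none | 47 | 0.880 | 0.900 | 2.0 |
| 25 patients, months 24 to 35.5 | 47 | 0.863 | 0.884 | 2.1 |
| 25 patients, months 0.5 to 35.5 | 30 | 0.824 | 0.855 | 3.1 |
| 25 patients, months 0.5 to 12 | 22 | 0.771 | 0.811 | 4.1 |

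If the missed patient were instead censored when the therapy starts, the shifts are 1.9, 1.9, 2.8 and 3.7. These are examples, not bounds.

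**4. Relapse date.**

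| Endpoint | Protocol date | SAP date |
|---|---|---|
| LRR | first evidence (8.4); first suspicious record if found on imaging (8.6) | first definitive evidence (7.7.2) |
| DRR | first suspicious record if found on imaging (8.6); 8.5 has no dating rule | first definitive evidence (7.7.3) |
| DFS | first occurrence (8.7), with 8.6 for imaging | first occurrence (7.7.4), no dating rule |

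Protocol 8.4 and 8.5 define suspicious and definite as separate classes of evidence, so the two dates differ whenever confirmation is delayed. If both fall before 3 years, or both after, the 3-year rate is unchanged apart from small effects of who is still at risk. If they straddle 3 years, one relapse drops out, which lowers LRR or DRR by the same 100/n: 1.7 to 2.5 points for n from 58 to 40, ignoring censoring. The protocol 5.0 schedule puts pelvic MRI at months 6, 18 and 30 and CT at 12, 24 and 36, so the exposed case is chiefly a suspicion at a month-36 assessment done slightly early and confirmed afterwards.

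**The case against.** The best defence on DFS is that the SAP's source list is merely incomplete. Table 31 counts non-protocol therapy by type with no form limit. The censoring sentence also has no form limit and is most naturally read as treating recipients as failures. Table 47 reports anti-cancer therapy in follow-up before relapse, so an omission could be noticed. The Relapse Report is due at relapse or failure and might hold the event. This shows the intention was probably the protocol's. It does not override an explicit list of source forms, and the text leaves two possible outcomes for the same patient.

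The event should also be uncommon. Protocol 8.7.1 requires a detailed work-up at first failure with sites documented, and therapy for a documented recurrence already counts through the relapse events. That stands, and it is why no count of affected patients can be given.

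On dating, *definitive* may be loose wording for evidence of a relapse later accepted as real: the SAP's parenthesis includes clinical evidence, whereas protocol 8.4 does not accept physical examination alone. Protocol 8.6 has suspicion-only dates reviewed centrally. That reading is possible, but it is not what 7.7.2 and 7.7.3 say.

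A reader might infer that waiting for the next scheduled scan moves relapse dates by many months and so biases the 3-year rates generally. The documents do not support this. The work-up in 8.7.1 and the first-relapse column of protocol 5.0 call for prompt investigation, and a shift on one side of 3 years hardly changes the rate.

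**Conclusion.** Both discrepancies are real and should be corrected. SAP 7.7.4 can miss a DFS failure that the protocol lists, and SAP 7.7.2 and 7.7.3 depart from the protocol's dating rule without saying so. For distant relapse the conflict is with 8.6 alone; for DFS the SAP is silent on dating rather than contradictory.

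The effect is about 1.7 to 2.5 points of 3-year DFS per missed failure for n from 58 to 40 without censoring, and more if censoring is heavy and early. For dating, it is a similar amount per relapse, but only where the two dates straddle 3 years. How many patients are affected is not in the documents and may be none.

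A reader might infer that the reported DFS will certainly be too high, that the SAP has redefined the endpoint, or that the trial's conclusion is at risk. None of these follows. The event may never occur, the SAP's definition otherwise matches the protocol's, and the organ preservation endpoint and its decision rule do not use these data.

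**What to change.** **SAP 7.7.4.** Add the Follow-Up Report, and the Relapse Report where it records a failure, as sources for the non-protocol-therapy event. Count only therapy dated after complete excision, and use the start of that therapy as the event date. State, consistently with protocol 8.7, how therapy given without recurrence is handled (for example, adjuvant therapy after TME), and give the censoring date for any recipient not counted as a failure.

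**SAP 7.7.2 to 7.7.4.** Require a relapse to be accepted as definite before it counts, but date it by protocol 8.4 and 8.6. Use the same date for LRR, DRR and DFS. Otherwise, state and justify the departure.

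**Cost.** SAP wording only: no new analysis set, table or figure. There are two cautions. The Follow-Up Report may bring in therapy given without recurrence, which 8.7 read literally would count, so that rule must be settled before the form is read. The CRF pages are not in the documents, so it could not be checked that a suspicion date is recorded separately from a confirmation date.

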7.8 Safety

The safety analyses will be based on the Chemotherapy Treated population defined in Section 6 unless otherwise specified. Adverse events and laboratories are graded and categorized using the NCI CTCAE except where CTCAE grades are not available.

7.8.1 Adverse Events

Adverse events (AEs) are recorded in the Adverse Events (AE) sections of CRF Chemotherapy Report, CRF Pre-Excision Report, CRF Surgery Report, CRF Follow Up Report (only AEs thought to be related to protocol treatment), and CRF Short Follow Up Report (ongoing or new grade 3 or higher AEs which are thought to be related to protocol treatment). Severity grade 5 will be combined with grade 4 for the purpose of this report. Adverse events reported during study treatment (in AE sections of CRF Chemotherapy Report, CRF Pre-Excision Report, and CRF Surgery Report) are defined as acute (on treatment) adverse events. Adverse events reported in AE section of CRF Follow Up Report and CRF Short Follow Up Report will be defined as delayed (long term) AEs.

Treatment (capecitabine, oxaliplatin, leucovorin, surgery, and radiotherapy) related adverse events are those events with a relation to protocol therapy of 3=possible,

4=probable or 5=definite.

Severe adverse events are those events reported with a NCI CTCAE Grade of 3 or higher.

The following variables are summarized:

- Acute adverse events: worst CTCAE grade per patient (**Table 32**)
- Severe acute adverse events: worst CTCAE grade per patient (**Table 33**)
- Treatment related acute adverse events: worst CTCAE grade per patient (**Table 34**)
- Delayed severe adverse events: worst CTCAE grade per patient (**Table 35**)

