LARS and the Fecal Incontinence Quality of Life Instrument		X		X			6, 12, 24 and 36		
Health Economics									
EQ-5D-5L		X	X ¹⁹	X		X	6, 12, 24 and 36		
Phone Contact									
Survival information								X	X
1. Timing for visits after excision are scheduled from last tumour excision date: a. For patients having TME as first protocol excision: from TME date b. For patients having TEMS/TAMIS as first protocol excision: from TEMS/TAMIS date c. For patients having TEMS/TAMIS as first protocol excision and then having a TME: from TME date 2. See protocol section 8 for definitions. 3. Phone contacts or visits after first disease relapse are required every 6 months from date of relapse. 4. Tests may be done on the date of treatment or, if not possible, the previous working day before treatment day. If treatment is to begin on a Monday, may be done on the previous Friday (maximum 72 hours prior to treatment). 5. Please also see protocol Section 12.0 and details for collection, processing, storing, and shipping these samples provided in the CO.28 Correlative Studies Manual. 6. Whole blood (that is not for ctDNA testing) will only be collected prior to enrollment. 7. Not required for patients that had a TME. 8. To be obtained within 28 days as close to the time of relapse as possible. Blood for correlatives done within 28 days PRIOR to date of relapse does not need to be repeated. 9. For CT pelvis and chest, a CT scan with contrast is preferred but not mandated. Patients with contrast allergies may undergo chest X-ray and /or Chest MRI. 10. Contrast is REQUIRED for the CT scan of the abdomen. Patients with contrast allergies may undergo liver ultrasound and /or MRI. 11. Rectal exam and proctoscopy are ideally to be performed by the primary surgeon. Proctoscopy should be performed ≤ 90 days prior to enrollment. Ideally, the surgeon should perform pre and post induction treatment proctoscopies. A gastroenterologist may perform proctoscopy in lieu of the surgeon, but then must also perform the follow-up exam. Proctoscopy may be accomplished using rigid proctoscopy or as part of a flexible sigmoidoscopy or colonoscopy. 12. For patients that had a TME it is only required at month 36. 13. If a rectal tumour tissue biopsy was performed within 90 days prior to enrollment, a repeat biopsy is not necessary. It is recommended that surgeons take a biopsy of the tumour during sigmoidoscopy/colonoscopy to ensure tissue availability and adequate pathology report confirming invasive well-moderately differentiated rectal adenocarcinoma and no evidence of pathologic high risk factors. 14. It is strongly encouraged that suspicious or unequivocal evidence of first local relapse be confirmed definitively by either biopsy (preferred) or by repeat/confirmatory imaging. Where imaging evidence of first local relapse is, in the opinion of the investigator and radiologist, absolutely unequivocal and not requiring subsequent confirmation by either biopsy or follow-up imaging, this must be clearly indicated in supporting documentation. 15. Urine pregnancy test in women of childbearing potential and if a false-positive is suspected this may include an ultrasound to rule-out pregnancy. 16. To be completed daily for patients receiving Capecitabine. 17. Adverse Events to be evaluated using the NCI Common Terminology Criteria for Adverse Events (CTCAE v5.0) (see Appendix III). 18. Only protocol chemotherapy or surgery related adverse events have to be reported after the 30 days post-excision visit. 19. After 3 cycles of FOLFOX or after 2 cycles of CAPOX.									

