10.3 Follow-up Off Protocol Treatment

All patients will be seen 30 days after excision and then at months 6, 12, 18, 24, 30, 36, 48 and from the excision date (please refer to section 5.0 for more details). Phone contacts at months 48 and 60 after excision will be acceptable.

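### Adverse events are called acute or delayed by form rather than by time: day-30 events probably count as long term, and grade 1–2 events on the Follow Up Report reach no adverse event table

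*SAP*

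**What the plan says.** SAP 7.8.1 assigns each adverse event to a period by its case report form. Entries made "in AE sections of CRF Chemotherapy Report, CRF Pre-Excision Report, and CRF Surgery Report) are defined as acute (on treatment) adverse events". For the later forms, entries on the "CRF Follow Up Report and CRF Short Follow Up Report will be defined as delayed (long term) AEs". Neither definition contains a date or an interval. The same section says that the Follow Up Report holds only events thought related to protocol treatment, and the Short Follow Up Report only related events of grade 3 or higher.

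Four summaries follow: acute events at all grades (Table 32), severe acute events (Table 33), treatment-related acute events at all grades (Table 34, repeated for each drug, for surgery and for radiotherapy) and severe delayed events (Table 35). Severe means grade 3 or higher.

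On the visit itself, protocol 10.3 states: "All patients will be seen 30 days after excision". The section 5.0 flowsheet schedules an adverse event assessment there. Footnote 18 adds: "Only protocol chemotherapy or surgery related adverse events have to be reported after the 30 days post-excision visit". That footnote is attached to the later columns of the flowsheet, not to the 30-day column.

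On the forms, protocol Appendix III describes the Follow-up Report as "Continued follow-up after chemotherapy, radiotherapy and/or protocol tumour excision(s) completed". It makes the Surgery Report due within 4 weeks "after surgery (either TME or TEMS/TAMIS"). SAP 7.9 lists "Concomitant medications for patients 30 days after excision (reported on CRF Follow-Up Report").

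**The concern.** A form is a poor stand-in for time since surgery. If the 30-day visit is recorded on the Follow Up Report, a surgical event first noted a month after excision is reported beside events from months 6 to 36. Protocol 9.1, for serious-event reporting, takes the treatment period to run until 30 days after the last protocol treatment, so such an event can fall inside the treatment period and still be labelled long term.

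The label also decides what is shown. Acute events are tabulated at every grade, delayed events only from grade 3. At stake is secondary objective 5, which covers the nature, severity and frequency of both acute and long-term toxicity.

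**Working it through.** The plan gives no figure to reproduce. The check follows an event from the visit to the form, from the form to the label, and from the label to the tables.

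**1. Visit to form.** SAP 7.8.1 names five forms that carry adverse events: Chemotherapy, Pre-Excision, Surgery, Follow Up and Short Follow Up. For a routine visit 30 days after excision:

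- SAP 7.9 takes that visit's concomitant medications from the Follow-Up Report.
- Appendix III describes the Follow-up Report as the form for contact once the excisions are complete.
- The Surgery Report is due within 4 × 7 = 28 days of surgery, and 28 < 30, so its due date falls before the visit.
- Appendix III reserves the short follow-up form for patients after relapse or failure and for those with no protocol excision.

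The Follow Up Report is therefore the most likely form. No sentence says so for adverse events.

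**2. Form to label.** Under SAP 7.8.1, whatever is on that form is delayed. An event already entered on the Surgery Report remains acute.

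**3. Label to tables.** Coverage of a related surgical event first recorded on the 30-day Follow Up Report:

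| Table | Content | Grade 1–2 | Grade 3+ |
|---|---|---|---|
| 32 | acute, all grades | no | no |
| 33 | acute, grade 3+ | no | no |
| 34, surgery version | acute, all grades | no | no |
| 35 | delayed, grade 3+ | no | yes, as delayed |
| 36–37 | laboratory data, Chemotherapy and Pre-Excision Reports | no | no |
| 39 | complication items, Surgery Report | no | no |

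The grade 1–2 event appears in none of them; the grade 3+ event appears once, as delayed. Tables 44 and 45 do use the Follow-Up Report, but for transfusions and major medical problems, which are not graded adverse events.

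**4. The gap after day 30.** Only the Short Follow Up Report is restricted to grade 3 or higher. The Follow Up Report takes related events of any grade at every visit, and the SAP tabulates only those of grade 3 or higher. The grade 1–2 gap therefore covers months 6 to 36 as well as day 30.

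**5. Scope of collection.** Footnote 18 restricts reporting to related events only after the 30-day visit. SAP 7.8.1 restricts the Follow Up Report to related events without that exception. If this form carries the visit, unrelated events at day 30 are required by the protocol and have no place on the form as the SAP describes it.

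**The case against.** The best reply is that the link from visit to form is an inference. SAP 7.9 speaks of concomitant medications. Four weeks is a submission deadline, not a stated data window, and nothing says that later events cannot be added to the Surgery Report. The conflict over related events can even be read the other way: if all events are collected up to the 30-day visit and the Follow Up Report takes only related ones, the unrelated ones need another form, and the Surgery Report is the only form after excision without that limit. The blank forms are not among the documents.

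This stands as a limit on certainty. If the Surgery Report does carry 30-day adverse events, the mislabelling disappears. The missing grade 1–2 table for delayed events remains, because it does not depend on where day-30 events are entered.

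It is also fair to say that sorting by form is explicit and reproducible, that these are descriptive tables in a single-arm trial, and that related grade 3+ events stay visible in Table 35. The primary endpoint and the stopping rule are untouched.

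Four stronger readings are tempting and are not supported:

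- *That early surgical toxicity as a whole moves to the late category.* Only events first recorded on the 30-day form would move.
- *That objective 4, post-operative complications, is distorted.* Table 39 uses dedicated Surgery Report items and does not use the acute or delayed label.
- *That long-term toxicity is overstated generally.* This can hold only at grade 3 or higher; delayed grade 1–2 events are not tabulated at all.
- *That up to 58 patients are affected.* That is total accrual, not a count of patients or events.

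**Conclusion.** The point holds in two parts of unequal certainty.

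The first is firm: related grade 1–2 events first recorded on any Follow Up Report appear in no adverse event table, so objective 5 is only partly answered. This follows directly from SAP 7.8.1 and the shell of Table 35.

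The second is likely but not stated outright: events first recorded at the 30-day visit are labelled long term. It assumes that this visit's adverse events are entered on the Follow Up Report. On that assumption, acute surgical toxicity is understated at all grades, and grade 3+ late toxicity may be overstated.

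The number of events cannot be derived from the documents. The conflict between SAP 7.8.1 and footnote 18 over unrelated events is real under the same assumption and needs to be reconciled. The matter should be corrected before the safety tables are produced.

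**What to change.** In SAP 7.8.1:

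1. State which form carries adverse events from the 30-day visit, and reconcile the related-only limit with protocol footnote 18.
2. Class as acute every event with onset up to and including the 30-day visit, timed from the last TEMS/TAMIS or TME, on any form. Class later onset as delayed.
3. For patients with no excision, who have no such visit, use 30 days after the last protocol treatment.
4. The documents do not say that onset dates were captured. If they were not, class events on the 30-day Follow-Up Report as acute; Table 46 already isolates that visit for medications.
5. Rebuild Tables 32–35 on this rule and add an all-grade table of delayed events. Moving the boundary alone would leave the grade 1–2 gap open after day 30. Note under the new table that the Short Follow Up Report collects only grade 3 or higher.
6. State as a limitation any unrelated 30-day events that were not collected; no change to the analysis can recover them.

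The cost is SAP wording and a little more programming. No new data are needed.
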